Secondary	Cognitive Elaboration of Smoking Harms		Χ			Χ	Χ		
Secondary	Cognitive Elaboration of Cessation Benefits	Χ		Χ	Χ			Χ	Χ
Secondary	Response Efficacy	Χ		Χ	Χ			Χ	Χ
Secondary	Perceived Susceptibility to Smoking Harms		Χ			Χ	Χ		
Secondary	Expressed Reactance Against Messages	Χ	Χ		Χ	Χ	Χ		
Secondary	Cigarettes Per Day (number of cig logs)	Χ	Χ	Χ	Χ	Χ	Χ	Χ	Х

X=included in the results data tables; results for outcomes that are not specific to hypotheses (i.e., no "X" in table above) are presented in data tables at the end of this document (see Appendix 1).

Assumptions for calculating power:

This section describes our assumptions regarding power before we collected our data. Throughout our discussion of power related to the statistical tests to evaluate our hypotheses of interest, we assume a moderate within-person autocorrelation of ρ = 0.40 for repeated measures. This estimate was lower than in the data we collected for this project (mean ICC=0.73) and in our re-assessment of preliminary data (mean ICC=0.72). Instead of running simulation programs to estimate power for mixed effects generalized linear models, we calculate the effective number of independent observations and use power for independence models.

Effective sample size: The effective number of independent observations $N_{\rm eff}$ is related to the number of correlated observations $N_{\rm eff}$ and the autocorrelation of correlated observations ρ as $N_{\rm eff} = N(1-\rho)/(1+\rho)$. Thus, our power calculations are derived using independence models with $N_{\rm eff} = 3N/7$ observations. Table 4 shows the effective sample for each hypothesis and data type, including adjustment for 10% and 20% missing data.

Table 4. Effective sample size for each hypothesis and data type, including missing data effects

				$N_{ m eff}$			
	Rep.			0% missing 10% missing 20% miss			
Data	Measures	Hypotheses	N	data	data	data	
Type 1	14	H1/H2	2,240=160*14	960	864	768	
	14	H3 ^{a-b} /H4 ^{a-b} /H5 ^{a-b} /H6 ^{a-b}	1,120=80*14	480	432	384	
Type 2	56	H1/H2	8,960=160*56	3,840	3,456	3,072	
	56	H3 ^{a-b} /H4 ^{a-b} /H5 ^{a-b} /H6 ^{a-b}	4,480=80*56	1,920	1,728	1,536	

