We use the numbers in Table 4 as inputs for independent observations in deriving the detectable effect. In what follows, we report ranges of detectable effect sizes from 0% to 20% missing data in complete-case analyses. This presentation notwithstanding, our data analysis will employ multiple imputation methods to replace missing data, and we will investigate sensitivity models to determine whether missingness is related to any of the outcomes or covariates (See **Missing Data**, below).

Alpha: Modifications of the level of significance are considered using Bonferroni adjustment to maintain an overall 0.05 level of significance. As most of our hypotheses involve assessing 6 primary outcomes for each of the two data types, we use a Bonferroni-corrected $\alpha = 0.05/6 = 0.0083$.

Effects size referents: We follow Cohen's standardized effect sizes of small=0.20, medium=0.50, and large=0.80.¹ Standardized effect sizes are absolute differences divided by the standard deviation.

Power: Power was fixed to 80% in all analyses.

Analyses: Most detectable effect sizes were calculated using PASS 2012 software from NCSS (Kayesville, Utah). The only exception is for a hypothesis of mediation. In that case, we used the *powerMediation* package for *R* software. Specifically, we utilized the *minEffect.SLR* method to determine the minimum detectable slope (effect).

All detectable effect sizes were calculated for power=80% and stated level of significance. Furthermore, we assessed detectable effect sizes for the planned data collection design, up to 10% missing data, and up to 20% missing data (see Table 4).

Statistical design:

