To test our study hypotheses (see Table 2, from Research Plan), we estimated a series of mixed effects generalized linear models, adjusting for repeated measures. The specific model we used depended on the type of dependent variable in the model. For each hypothesis, we estimated mixed effect generalized linear model of the outcome as a function of the inverse link: mixed-effects ordered logistic regression with inverse logit link for continuous/ordinal measures; mixed-effects regression with identity link for continuous/ordinal measures; negative binomial regression with log link for count measures; and mixed-effects logistic regression with inverse logit link for binary measures. Also, for outcomes with response options from 1 to 7, we estimated both mixed effects linear regression and ordered logistic regression models; however, we only report the results for the ordered logistic regression due to concerns about the distribution of responses and because the results are consistent across models. Note that the one count measure that we evaluate (i.e., cigarettes per day) is a single measure for each person and so there are no repeated measures. Evaluation of hypotheses will involve inference from Wald tests of associated regression parameters. We present power calculations for each hypothesis along with the model used to conduct the statistical tests. Subsequently, we discuss missing data and sensitivity analyses.

Throughout the following sections, we present models using the following indicator variables:

InsY _i	Person i has cigarette packages with inserts
$PicY_i$	Person i has cigarette packages with HWLs that include text and pictures
SeHi _i	Person i has a high baseline self-efficacy measure
EdHi _i	Person i has a high baseline education measure
$LtHi_i$	Person i has a high baseline literacy measure

Similarly, we also use the following indicator variables:

InsN _i	Person i has cigarette packages without inserts
$PicN_i$	Person i has cigarette packages with HWLs that include text only
$SeLo_i$	Person i has a low baseline self-efficacy measure
$EdLo_i$	Person i has a low baseline education measure
$LtLo_i$	Person i has a low baseline literacy measure

Model 1:

$$y_{ij} = g^{-1} \big[\beta_0 + (InsN_i \times PicN_i)\beta_1 + (InsN_i \times PicY_i)\beta_2 + (InsY_i \times PicN_i)\beta_3 + (InsY_i \times PicY_i)\beta_4 + Z_{ij}\tau + \gamma_i + \epsilon_{ij} \big]$$

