where g^{-1} is the inverse link function (identity for continuous measures, log for count measures, and inverse logit for binary and ordinal measures), Z_{ij} is a possibly time-varying vector of covariates (e.g., sex, race, age, nicotine dependence, quit intentions), and y_{ij} is the outcome for the ith person at the jth repeated measure. This model will be used for evaluating Hypotheses 1 ($\mu_{InsN} = \mu_{InsY}$), 2 ($\mu_{PicN} = \mu_{PicY}$), 3a ($\mu_{PicN,InsY} = \mu_{PicY,InsY}$) & 4a ($\mu_{PicY,InsY} = \mu_{PicY,InsY}$) as shown in Table 5.

Table 5. Hypotheses evaluated using Model 1 and associated tests

Hypothesis	Test
Hypothesis 1	$H_0^1: \beta_1 + \beta_2 = \beta_3 + \beta_4$
Hypothesis 2	$H_0^2: \beta_1 + \beta_3 = \beta_2 + \beta_4$
Hypothesis 3a	$H_0^{3a}: \beta_3 = \beta_4$
Hypothesis 4a	$H_0^{4a}: \beta_4 = \beta_2$

Allowing up to 20% missing data, the range of effect sizes for which we will have 80% power to reject hypotheses are given by the values in Table 6 for the data type outcomes and specified level of significance.

Table 6. Level of significance and detectable effect sizes for all hypotheses

Hypotheses	Outcome	Level of significance	Range of effects*
H1 & H2	Type 1	$\alpha = 0.05/6 = 0.0083$	0.15 - 0.17
	Type 2	$\alpha = 0.05/6 = 0.0083$	0.07 - 0.08
H3a, H3b, H4a, H4b, H5a, H5b, H6a, H6b	Type 1	$\alpha = 0.05/6 = 0.0083$	0.22 - 0.24
	Type 2	$\alpha = 0.05/6 = 0.0083$	0.10 - 0.11

^{*}range of effects is for the different amounts of missing data (i.e., 0% - 20%)

Model 2a and Model 2b:

$$y_{ij} = g^{-1} \big[\beta_0 + InsN_i \beta_1 + \, InsY_i \beta_2 + Z_{ij} \tau + \, \gamma_i + \epsilon_{ij} \big]$$

Where g^{-1} is the inverse link function (identity for continuous measures, and inverse logit for binary and ordinal measures), Z_{ij} is a possibly time-varying vector of covariates (e.g., sex, race, age, nicotine dependence, quit intentions), and y_{ij} is the outcome for the ith person at the jth repeated measure. The 2a and 2b models are stratified over whether pictures were included (2a) or not (2b). This model will be used to assess Hypothesis

 $3b - H_0^{3b}$: $\mu_{InsN} = \mu_{InsY}$. Associated power is shown in Table 6. Note that the stratified analyses in Models 2a and 2b are investigated only if H_0^{3a} is rejected.

Note: H_0^{3a} was never rejected.

Model 3a and Model 3b:

$$y_{ij} = g^{-1} [\beta_0 + PicN_i\beta_1 + PicY_i\beta_2 + Z_{ij}\tau + \gamma_i + \epsilon_{ij}]$$

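### Table 6's detectable effects do not follow from its printed alpha of 0.0083; at those effects power is about 66% to 78%, not 80%, on the SAP's own inputs

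*SAP*

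**What the plan says.** Under Assumptions for calculating power, the SAP fixes each input:

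- **Sample size.** Repeated measures are converted to effective independent observations by N_eff = 3N/7, with results in Table 4: "Thus, our power calculations are derived using independence models with" that N_eff.
- **Alpha.** "As most of our hypotheses involve assessing 6 primary outcomes for each of the two data types, we use a Bonferroni-corrected" level of 0.05/6 = 0.0083. Table 6 repeats 0.0083 in all four rows.
- **Power.** "Power was fixed to 80% in all analyses".
- **Method.** "All detectable effect sizes were calculated for power=80% and stated level of significance".

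Under Statistical design, the SAP then says that "the range of effect sizes for which we will have 80% power to reject hypotheses are given by the values in Table 6". The printed ranges, from 0% to 20% missing data, are 0.15-0.17 (H1/H2, Type 1), 0.07-0.08 (H1/H2, Type 2), 0.22-0.24 (H3-H6, Type 1) and 0.10-0.11 (H3-H6, Type 2). Sidedness is not stated; the tests are described only as follows: "Evaluation of hypotheses will involve inference from Wald tests of associated regression parameters".

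**The concern.** All the inputs are given except sidedness, so the table should be reproducible from the page. It is not, and the printed effects are smaller than 0.0083 allows. They correspond to a more lenient test: 1.5 times the stated alpha for Type 1 data (0.0125/0.0083) and three times for Type 2 data (0.025/0.0083).

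The SAP reports that H3a and H4a were never rejected, and it refers to Table 6 for the power behind Models 2 to 5. A reader weighing those null results would credit the tests with 80% power at effects where the stated rule gives less.

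**Working it through.** **Inputs.** N_eff per group from Table 4 (0% / 20% missing): 960 / 768 and 3,840 / 3,072 for H1/H2 (Type 1, Type 2); 480 / 384 and 1,920 / 1,536 for H3-H6. Table 4 itself reproduces: for example 2,240 × 3/7 = 960, and 960 × 0.8 = 768. Effects are standardized (SD = 1), groups are equal (80 per cell, 160 per factor level), and power is 80%. Two-sided testing is assumed.

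**Formula.** Detectable effect = (z₁₋α/₂ + 0.8416) × √(2/n). The z values are 2.638 for α = 0.05/6, 2.498 for 0.0125 and 2.241 for 0.025. Example: (2.638 + 0.8416) × √(2/960) = 0.159. Using the noncentral t instead changes the results by less than 0.001.

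**Detectable effects (0% to 20% missing).**

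| Row | Printed | α = 0.0083 | α = 0.0125 | α = 0.025 |
|---|---|---|---|---|
| H1/H2, Type 1 | 0.15-0.17 | 0.159-0.178 | **0.152-0.170** | 0.141-0.157 |
| H1/H2, Type 2 | 0.07-0.08 | 0.079-0.089 | 0.076-0.085 | **0.070-0.079** |
| H3-H6, Type 1 | 0.22-0.24 | 0.225-0.251 | **0.216-0.241** | 0.199-0.223 |
| H3-H6, Type 2 | 0.10-0.11 | 0.112-0.126 | 0.108-0.121 | **0.100-0.111** |

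Bold marks the ranges that match print to two decimals. At 0.0083 only one of eight endpoints matches (0.2246, printed 0.22).

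**Power at the printed effects, α = 0.0083.** Power = Φ(d√(n/2) − 2.638). Example: Φ(0.10 × √960 − 2.638) = Φ(0.460) = 0.677.

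| Row | 0% missing | 20% missing |
|---|---|---|
| H1/H2, Type 1 | 74.2% | 75.6% |
| H1/H2, Type 2 | 66.6% | 69.0% |
| H3-H6, Type 1 | 77.9% | 75.4% |
| H3-H6, Type 2 | 67.7% | 65.9% |

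**A check that does not depend on sidedness.** Type 2 N_eff is exactly four times Type 1 N_eff (1,920/480 and 1,536/384). At one common alpha and power, the Type 2 effect must therefore be half the Type 1 effect. For H3-H6, with rounding stretched as far as it goes in the table's favour, the printed ratios are at most 0.105/0.215 = 0.488 and 0.115/0.235 = 0.489. No single alpha can produce both H3-H6 rows.

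**Other readings tried.**

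- One-sided 0.0083 gives 0.148-0.165 and 0.074-0.083 for H1/H2, which match, but 0.209-0.234 and 0.104-0.117 for H3-H6, which do not.
- Truncating instead of rounding at two-sided 0.0083 matches only the H1/H2 rows.
- Treating N_eff as a total across both groups matches no row.

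**The case against.** Several points on the other side have weight.

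- **Rounding.** The printed effects carry two decimals, and 0.01 is about 14% of 0.07. With 0.005 added to every entry, power at 0.0083 becomes 77.6% / 78.6%, 74.2% / 75.6%, 80.2% / 77.5% and 73.1% / 70.8% for the four rows in order. Rounding thus explains part of the shortfall, but seven of eight endpoints stay below 80%.
- **The cause is inferred.** The SAP's note on its revisions does not mention alpha. The alphas that fit are not unique either: after rounding, roughly 0.0107 to 0.0128 serves both Type 1 rows and 0.019 to 0.036 both Type 2 rows. The values 0.05/4 and 0.05/2 are simply the natural Bonferroni levels in those intervals. That the table does not match its alpha column does not depend on this explanation.
- **Sidedness is unstated.** One-sided testing would put power at the printed effects at 74% to 84%, but it does not reproduce the H3-H6 rows. The appendix p-values also look two-sided: for worry under H1, 0.77/0.59 = 1.31, which gives a two-sided p of 0.19, as printed.
- **H5 and H6 are not simple two-group contrasts.** They compare differences between subgroups, so the power figures above for the H3-H6 rows are not the power of those tests. This stands as a limit on the recomputed figures.
- **A larger, disclosed problem exists.** The SAP says the observed mean ICC was 0.73 against an assumed 0.40. In its own formula, 0.73 at α = 0.0083 gives about 0.26-0.29 (Type 1) and 0.13-0.15 (Type 2) for H1/H2. That gap is bigger than this one, but it is a matter of assumption; the point here is that the table does not follow from the assumptions the SAP did make.

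**Conclusion.** Table 6 is wrong as written. On the SAP's own N_eff, 80% power and two-sided 0.0083, seven of eight endpoints are too small. The largest gap is the 0.11 endpoint, where the correct value is 0.126, about 14% larger; put the other way, the printed value is about 12% too small. Power at the printed effects runs from 65.9% to 77.9%. In absolute terms the gaps are under 0.02 SD: H1/H2 stay below Cohen's small effect of 0.20, and H3-H6 with Type 1 data stay just above it.

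The power range assumes two-sided tests and simple two-group contrasts, and takes the printed effects at face value. It accepts the N_eff formula and ρ = 0.40 as given and does not assess them. For the H3-H6 rows, the conflict with a single common alpha holds whichever side convention was used.

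**What to change.** Recompute every entry of Table 6 at the alpha actually used for testing, print that alpha, and state whether tests are one- or two-sided. If 0.0083 two-sided stands, with the present N_eff, the simple-contrast ranges are 0.16-0.18 and 0.08-0.09 (H1/H2, Type 1 and Type 2) and 0.22-0.25 and 0.11-0.13 (two-cell contrasts such as H3a and H4a). If the effects were meant for 0.0125 and 0.025, correct the alpha column and the Alpha paragraph instead, and explain why the levels differ by data type. Give H5 and H6 their own rows, computed for the subgroup contrasts they test.

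The cost is one table and a sentence or two in the SAP. No data or test result changes if testing was done at 0.0083; the stated sensitivity becomes slightly less favourable.

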1 PROTOCOL SUMMARY

Title:	Evaluation of cigarette package inserts for enhanced communication with smokers
Grant Number:	R01 CA215466
Study Description:	A randomized controlled trial was conducted to assess the influence of cigarette package inserts with messages about the benefits of cessation and tips for quitting on smoking cessation- related psychosocial and behavioral outcomes. We hypothesized that inserts would promote these outcomes and that these effects would be enhanced when cigarette packages included both inserts and pictorial warning labels. In this 2X2 between-subject trial (i.e., inserts with efficacy messages vs. no inserts; pictorial warnings vs. text-only warnings), participants received a 2-week supply of their preferred cigarette brand variety, with labeling to reflect their experimental condition.
Objectives:	To evaluate the impact of inserts on smoking cessation-related outcomes using a randomized controlled trial among adult smokers.
Endpoints:	Data were collected over 14 days using a study smartphone. Participants were instructed to log every cigarette they smoked during this period. Approximately 4-5 times a day, participants were prompted to complete a brief, 1-3 minute survey immediately after they indicated that they had smoked, with cigarette logs sampled using an algorithm based on self- reported baseline smoking frequency. Each evening, between 7 and midnight, participants were instructed to respond to an evening survey using the smartphone app, which took 1-3 minutes to complete.
	Primary Endpoints : Self-efficacy to Quit Smoking; Self-efficacy to Cut Down on Smoking; Worry About Harms from Smoking; Strength of Feeling About Smoking; Extent of Motivation to Quit; Talk About Smoking Cessation or Harms; Foregoing or stubbing out a Cigarette
	Secondary Endpoints : Strength of Hopefulness About Quitting; Satisfaction From Smoking; Cognitive Elaboration of Smoking Benefits; Cognitive Elaboration of Smoking Harms; Cognitive Elaboration of Cessation Benefits; Response Efficacy; Perceived Susceptibility to Smoking Harms; Cigarettes Per Day

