Study Population:	Adult smokers in South Carolina and New York were recruited, with efforts to recruit people from lower socioeconomic status groups. Of 1818 people screened, 602 were ineligible, 773 either declined to participate or were unable to be scheduled for orientation, and 443 were eligible and randomized. Of these, 56 did not attend the study orientation, and 20 did not complete minimum criteria to be included in the analytic sample. The final analytic sample involved 367 people.
Description of Study Intervention/Experimental Manipulation:	The 2X2 between subject intervention involved randomization to one of four groups: a) control; b) inserts only; c) pictorial warnings only; d) inserts and pictorial warnings. Insert conditions included four rotating messages, two about cessation benefits and two with cessation tips. Warning text for all conditions included four rotating messages, with the text-only "control" condition used the current warning size and placement (i.e., 50% of one pack side), whereas pictorial warnings covered approximately 50% of the lower half of both the front and back of packs.
Study Duration:	June 28, 2019 to June 29, 2021
Participant Duration:	Study participation involved a 45-minute study orientation where potential participants completed a baseline survey, received training in the 14-day study, and were provided the study materials (i.e., smartphone, cigarette packs). After the 14-day observation period, participants completed a final survey and interview and received compensation.

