Expressed Reactance Against Messages ⁵	1.21	0.78	0.35	4.25	0.76

^{*}All results from ordered logistic regression mixed effects models except for "Expressed reactance" which shows Odds Ratio for logistic regression mixed effects model.

^{1.} response options=1 Not at all – 7 Extremely; 2. response options=1 very BAD – 7 Very GOOD; 3. response options=1 Not at all – 7 All the time; 4. 1 No chance – 7 Certain to happen.

^{1.} response options=1 Not at all -7 Extremely; 2. response options= 1 Not at all -7 All the time; 3. 1 No chance -7 Certain to happen.

^{1.} response options=1 Not at all - 7 Extremely; 2. response options=1 very BAD - 7 Very GOOD; 3. response options=1 Not at all - 7 All the time; 4. 1 No chance - 7 Certain to happen. 5. Response options=yes, no

Table 4. Hypothesis 4. Results for outcomes not specific to hypothesized effects

Outcome Variable name	Coef*	SE	95% CI LB	95% CI UB	p-value
Worry About Harms from Smoking ¹	-0.12	0.84	-1.77	1.53	0.88
Strength of Feeling About Smoking ²	-0.08	0.68	-1.41	1.26	0.91
Satisfaction From Smoking ¹	-0.07	0.56	-1.17	1.03	0.90
Cognitive Elaboration of Smoking Benefits ³	0.23	0.49	-0.74	1.19	0.65
Cognitive Elaboration of Smoking Harms ³	0.18	0.49	-0.78	1.14	0.71
Perceived Susceptibility to Smoking Harms ⁴	-0.15	0.66	-1.45	1.15	0.82

^{*}All results from ordered logistic regression mixed effects models

Table 5a. Hypothesis 5a. Results for outcomes not specific to hypothesized effects

Outcome Variable name	Coef*	SE	95% CI LB	95% CI UB	p-value
Self-efficacy to Quit Smoking ¹	0.50	0.97	-1.41	2.41	0.61
Self-efficacy to Cut Down on Smoking ¹	0.35	0.95	-1.50	2.21	0.71
Strength of Hopefulness About Quitting ¹	1.18	1.25	-1.27	3.62	0.35
Satisfaction From Smoking ¹	-0.31	0.79	-1.85	1.24	0.70
Cognitive Elaboration of Smoking Benefits ²	0.54	0.60	-0.64	1.72	0.37
Cognitive Elaboration of Cessation Benefits ²	0.37	0.67	-0.94	1.69	0.58
Response Efficacy ³	-0.42	0.77	-1.92	1.09	0.59

^{*}All results from ordered logistic regression mixed effects models

Table 5b. Hypothesis 5b. Results for outcomes not specific to hypothesized effects

Outcome Variable name	Coef*	SE	95% CI LB	95% CI UB	p-value
Self-efficacy to Quit Smoking ¹	0.57	1.38	-2.15	3.28	0.68
Self-efficacy to Cut Down on Smoking ¹	0.08	1.35	-2.56	2.73	0.95
Strength of Hopefulness About Quitting ¹	-1.38	1.77	-4.84	2.09	0.44
Satisfaction From Smoking ¹	-0.05	1.12	-2.25	2.15	0.97
Cognitive Elaboration of Smoking Benefits ²	1.67	0.86	-0.01	3.35	0.05

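### The insert effect on text-only packs is neither tested nor shown in the SAP: its only route is gated by H3a, a picture contrast that cannot say whether insert effects differ by warning type

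*SAP*

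**What the plan says.** In the SAP's Statistical design section, Model 1 has one coefficient per cell: β1 no insert/text-only, β2 no insert/pictorial, β3 insert/text-only, β4 insert/pictorial. Table 5 takes four tests from it:

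- H1, the insert effect averaged over warning types: β1 + β2 = β3 + β4.
- H2, the picture effect averaged over insert status: β1 + β3 = β2 + β4.
- H3a, the picture effect among insert packs: "H_0^{3a}: \beta_3 = \beta_4".
- H4a, the insert effect among pictorial packs: β4 = β2.

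Insert effects by warning type (H3b) are assigned to a second pair of models: "The 2a and 2b models are stratified over whether pictures were included (2a) or not (2b"). Their use is conditional: "Note that the stratified analyses in Models 2a and 2b are investigated only if" H3a is rejected. A note adds that H3a "was never rejected". Models 3a and 3b are gated in the same way on H4a, which was also never rejected.

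H3 (SAP Table 2; Protocol Table 1 of hypotheses) predicts larger insert effects with pictorial than with text-only warnings. The Protocol Summary gives the objective as "To evaluate the impact of inserts on smoking cessation-related outcomes using a randomized controlled trial among adult smokers" and says that the text-only control "condition used the current warning size and placement (i.e., 50% of one pack side").

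**The concern.** H3 compares two insert effects: β4 − β2 on pictorial packs and β3 − β1 on text-only packs. The first is tested as H4a. The second is absent from Table 5, and the one model that would give it sits behind H3a.

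That gate does not match what it guards. β3 = β4 compares warning types when an insert is present and says nothing about packs without one. It can hold while insert effects differ sharply by warning type (if β1 and β2 differ), and it can fail while they are equal. The contrast that addresses H3 is the interaction (β4 − β2) − (β3 − β1), which is not in Table 5.

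At stake is how the insert result is read. A reader of the SAP sees an average and one of its two components. The missing component concerns the packs whose warning size and placement are those in current use. The SAP's later correction (text before Table 7) revises H5 and H6 but states that H1 to H4 were correctly specified, so it does not deal with this.

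**Working it through.** **Inputs.** Coefficients and SEs (log-odds, mixed ordered logistic models) from SAP Appendix 1, Table 1 (H1) and Table 4 (H4), for the six outcomes printed in both.

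**Reproducing the printed figures.** Worry under H1 is printed as 0.77 (SE 0.59), 95% CI −0.38 to 1.92, p = 0.19. Then 0.77 ± 1.96 × 0.59 gives −0.39 to 1.93, and z = 0.77/0.59 gives p = 0.192. All 18 rows for these six outcomes in Tables 1, 3 and 4 agree within rounding.

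**Scale.** If H1 is printed as the average of two simple effects and H4 is a single cell-against-cell contrast, SE(H4)/SE(H1) should be about √2 = 1.41. If H4 were an interaction, the ratio would be 2. For worry, 0.84/0.59 = 1.42. The ratio is 1.42 to 1.44 for five outcomes and 0.49/0.30 = 1.63 for elaboration of smoking benefits, which fits less well.

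**Formulas.** With H1 = ½[(β3 − β1) + (β4 − β2)] and H4 = β4 − β2:

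- Text-only insert effect: β3 − β1 = 2·H1 − H4, with SE = √(4·SE(H1)² − SE(H4)²), treating cells as independent.
- Interaction: (β4 − β2) − (β3 − β1) = 2·(H4 − H1), with SE = 2·SE(H1).

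Worry: 2(0.77) − (−0.12) = 1.66. SE = √(4 × 0.59² − 0.84²) = √(1.392 − 0.706) = 0.83. Interaction: 2(−0.12 − 0.77) = −1.78, SE 1.18.

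| Outcome | H1 (SE) | H4 (SE) | Text-only effect (SE), p | Ratio to H1 | Interaction (SE), p |
|---|---|---|---|---|---|
| Worry (primary) | 0.77 (0.59) | −0.12 (0.84) | 1.66 (0.83), 0.045 | 2.16 | −1.78 (1.18), 0.13 |
| Feeling (primary) | −0.70 (0.48) | −0.08 (0.68) | −1.32 (0.68), 0.051 | 1.89 | 1.24 (0.96), 0.20 |
| Satisfaction | −0.38 (0.39) | −0.07 (0.56) | −0.69 (0.54), 0.20 | 1.82 | 0.62 (0.78), 0.43 |
| Harm elaboration | 0.59 (0.34) | 0.18 (0.49) | 1.00 (0.47), 0.034 | 1.69 | −0.82 (0.68), 0.23 |
| Susceptibility | 0.71 (0.46) | −0.15 (0.66) | 1.57 (0.64), 0.014 | 2.21 | −1.72 (0.92), 0.06 |
| Smoking-benefit elaboration | −0.09 (0.30) | 0.23 (0.49) | −0.41 (0.35), 0.24 | not informative | 0.64 (0.60), 0.29 |

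The last ratio (4.6) divides by an average near zero and means nothing.

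**Sensitivity to how the rows are read.** The appendix does not state the sign of each contrast. If Table 4 is coded in the opposite direction to Table 1, the five ratios become 1.8 to 2.3, and harm elaboration becomes 2(0.59) + 0.18 = 1.36, z = 1.36/0.47 ≈ 2.9, p about 0.004. That is the only value among the six below 0.0083, and it depends on the reversed sign. If the Table 3 rows were the pictorial-pack insert effects instead, the five ratios would be 1.9 to 3.6.

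**The case against.** The average over the other factor is a legitimate factorial estimand, and presenting simple effects only after a preliminary test is a recognised choice. Model 1 already estimates every cell. The SAP also says that results for hypothesised outcomes are in data tables outside this document, so absence can be asserted only for the SAP. All of this stands, but none of it defends this particular gate. A condition for showing simple insert effects should concern their difference, and H3a does not.

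The numbers also invite stronger readings that the documents do not support:

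- A reader might infer that insert effects are withheld for both warning types. They are not: H4a is the pictorial-pack effect, tested without a gate and printed for these six outcomes.
- A reader might infer that inserts work twice as well on text-only packs. When one of two averaged effects is near zero, the other is about twice the mean by arithmetic. None of the implied interactions is significant, so these data do not distinguish that pattern from a common insert effect.
- A reader might extend the ratio to the outcomes inserts were meant to change. Appendix 1 Table 1 holds only outcomes without an H1 mark in SAP Table 3. The documents give no figures for self-efficacy, motivation, talk or foregoing/stubbing.
- A reader might equate the text-only arm with current US labelling. The Protocol claims this only for size and placement. Its section 5 says that the wording came from the 2009 Act and was placed on stickers over the existing warning.

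**Conclusion.** The point holds as a reporting gap. β3 − β1 is not tested or shown in the SAP, and the condition that kept it out, H3a, is a picture contrast that cannot show whether insert effects differ by warning type. That is the question H3 asks.

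On the direct reading of Appendix 1, the implied text-only insert effects are about 1.7 to 2.2 times the printed average for five of six outcomes, with nominal p from 0.014 to 0.24 across all six. None reaches 0.0083, and the smallest interaction p is about 0.06. The figures show what the SAP leaves out. They are not evidence that inserts work on text-only packs, and they do not undermine the H1 test.

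This rests on three assumptions: that Table 4 carries Table 5's H4a contrast with the same sign as Table 1, that H1 is printed as an average (supported by the SE ratios in five of six rows), and that cells are approximately independent.

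**What to change.** Replace the gated Models 2a/2b and 3a/3b with contrasts from the fitted Model 1. For every primary outcome, report unconditionally, with confidence intervals:

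- insert effects: β3 − β1 (text-only packs) and β4 − β2 (pictorial packs);
- picture effects: β2 − β1 (no insert) and β4 − β3 (insert);
- the interaction (β4 − β2) − (β3 − β1).

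Label them as estimates outside the 0.0083 tests, and state the direction of each contrast.

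Do not simply lift the gate on Model 3. As written, it fits a picture effect within strata defined by pictures, where the predictor is constant and the effect cannot be estimated. Describe the text-only arm by its current warning size and placement, not as current US labelling.

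The cost is a few contrast statements per outcome from models already fitted, with no new data. The downside is more estimates to display, which is why the estimation-only label is needed.
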